8.1 Study Rational

Cardiovascular disease is one of the leading causes of mortality in the United States hence, there is an increasing demand for supplements to lower atherogenic lipid levels.

8.2 Investigational Product

The investigational product iwi/Cholesterol is a commercially available capsule-form herbal (algae) supplement containing Almega®PL, a *Nannochloropsis* algae-derived extract rich in eicosapentaenoic acid (EPA). EPA is a type of omega-3 essential fatty acid known to play a beneficial role in protection against cardiovascular disease. lwi/Cholesterol is the only source of long chain omega-3 that does not contain the DHA that is present in other omega-3 sources (fish oil, krill oil, other algal oils). Almega®PL was registered at the Food and Drug Administration (FDA) as a New Dietary Ingredient (NDIN) in 2014.

8.3 Background

AlmegaPI was previously studies in a double-blind, placebo-controlled, randomized three-month clinical trial (Rao et al., 2020 *Nutrients*, 12, 1869) that showed that this product decreases total cholesterol and VLDL-cholesterol.

8.3 Risk Benefit Assessment

8.3.1 Known Potential Risks

The safety of Almega®PL has already been reviewed by the FDA as part of the New Dietary Ingredient notified in 2014. AlmegaPl is a commercial rather than an investigational product with more than 5 years of history of use, where no major adverse events have been reported. In the above-mentioned clinical trial (Rao et al., 2020 *Nutrients*, 12, 1869) three participants in each group (placebo and Almega®PL) reported adverse effects (nausea, abdominal cramping and diarrhea) which was likely associated to the nocebo effect.

8.3.2 Known Potential Benefits

- Almega®PL decreases total and VLDL-cholesterol (Rao eta al., 2020)
- AlmegaPL increases your omega-3 index (Rao et al., 2020).
- Higher bioavailability than other omega-3 forms (Kagan et al., 2013 Lipids Health Dis, 12, 1)
- No fishy aftertaste.
- More sustainable than fish oil.
- Provides each participant with their lipid panel information they could monitor during the study.
- Increase consumer awareness and engagement towards Almega®PL and their health benefits.

8.3.3 Assessment of potential risk and benefits Potential Risks

As a final remark we would like to add that the current study will be targeting new customers that will be taking the Almega®PL regardless of their participation of this study. Therefore, the study is not exposing the participants to the risks (and benefits) of taking the supplement but rather monitoring the population that is already taking the supplements. From that point of view, this is not strictly an interventional study, but a cohort study in which a population is being monitored.

8.3 Objectives and Endpoints

The aim of this study is to assess the effectiveness of Almega®PL on improving blood markers associated with heart health of iwi customers. Specifically, we would like to confirm the decrease in cholesterol observed in our previous trial (Rao et al., 2020) while assessing the capacity to decrease also triglycerides (primary outcome). As a secondary objective we would like to understand if EPA, precursor of signalling molecules involved in the inflammatory response, could help decrease the inflammatory marker hs-CRP.

OBJECTIVES	ENDPOINTS	JUSTIFICATION FOR
		ENDPOINTS
Primary		
,		
Can Almega®PL supplement	Triglyceride change from baseline	Triglyceride levels is
decrease triacylglycerides in a	over 6-month period.	an atherogenic lipid
generally healthy population?	-	and an important risk
9 1 9 9 1 9 1 9 1		factor in
		Cardiovascular
		Disease
Secondary		2.500.50
Secondary		
Can Almega®PL supplement	Total Cholesterol change from	Cholesterol in plasma
replicate the decrease in VLDL and	baseline over 6-month period.	levels is atherogenic
total cholesterol we observed in	VLDL-Cholesterol change from	and a risk factor in
our previous clinical trial (Rao et	baseline over 6-month period.	Cardiovascular
al., 2020)?	LDL-Cholesterol change from	Disease.
Will the results from a controlled	baseline over 6-month period.	Hs-CRP is an age
population translate to the iwi	HDL-Cholesterol change from	related inflammatory
costumers?	baseline over 6-month period.	market. Omega-3 help
Can Almega®PL supplement	hs-CRP change from baseline over	regulate the
decrease the age-related	6-month period.	inflammatory
inflammatory marker hs-CRP in a	Fasting glucose change from	response.
generally healthy population?	baseline over 6-month period.	•
	HbA1c change from baseline over	
	6-month period.	

OBJECTIVES	ENDPOINTS	JUSTIFICATION FOR ENDPOINTS

9. Study Design:

EPA is a type of omega-3 essential fatty acid known to play a beneficial role in protection against cardiovascular disease. Almega®PL is the only natural source containing EPA as sole n-3 HUFA that is available over the counter for human consumption. We **hypothesized** that AlmegaPL supplementation improves blood markers associated with heart health and inflammation. This post-market open label single armed trial involving 200-300 male and female participants, that will be monitored during the first 6 months following their subscription to Almega®PL.

As part of the **screening procedure**, participants will complete a short questionnaire to make sure they are new iwi users. Any participant who is already using iwi will not be considered in the study. Any participant that has a serious condition (including but not limited to kidney, neurological, immunological, liver, and gastrointestinal disease, any heart condition, or diabetes) will also be disqualified for the program and directed to their doctor. Any participant attempting conception, pregnant or breastfeeding will also be disqualified. All other participants will be accepted into the limited study based on their time of application until the quota is completed. Participation in this study is purely voluntary and participants can withdraw at any point without prejudice.

Participants will be asked to take the allocated product according to the **dose** prescribed (2 capsules per day containing 1000-1100 mg Almega®PL) and adherence to the protocol will be evaluated with a follow up email. Participants will be asked to maintain their usual level of physical activity and diet for the duration of the study. The dose used in this trial is in agreement with the commercial dose communicated to the FDA and comparable to doses previously used in our clinical trials.

Along with the fist supplement order shipped to the new subscriptions, participants will receive the baseline hearth health test kit from ImawareTM. Participants will be contacted 3 and 6 months after and they will be sent subsequent kits once the confirmed adherence to the supplement. The test kits will monitor blood lipid levels across a supplementation period (baseline, month 3 and month 6) thanks to a finger prick blood drawing system. The age, height, weight, gender, fasting total cholesterol, LDL-cholesterol, HDL-cholesterol, calculated VLDL-cholesterol, triglycerides, as well as hs-CRP inflammatory marker, and glucose and HbA1c as diabetes indicator of each participant will be recorded over the study period. Qualitas Health will receive the aggregated data of the participants only for statistical analyses at their headquarter in Houston and store it in the company share drive with access restricted to those involved in the study. There will be no cost incurred for this analytical assessment to the participant.

Results for the per protocol (PP) population will be first tested for normality before any other test will be conducted and baseline data was compared again month 3 and month 6 data. Based on the distribution of data, Welch two-sample unequal variance t-tests and Wilcoxon Ranks sum tests were used to compare two-tailed differences between groups. Differences will be considered statistically significant at a p value < 0.05. Intervention effect will also test using an analysis of covariance model (ANCOVA) adjusting for baseline parameters.

10. Study Procedures:

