### 1.1. Study objectives and endpoints

4-Mar-2022

The aim of this study is to assess the effectiveness of Almega®PL on improving blood markers associated with heart health of iwi customers. Specifically, we would like to confirm the decrease in cholesterol observed in our previous trial (Rao et al., 2020) while assessing the capacity to also decrease triglycerides (primary outcome). As a secondary objective we would like to understand if EPA, precursor of signalling molecules involved in the inflammatory response, could help decrease the inflammatory marker hs-CRP.

Objectives and related endpoints are described in Table 1-1 below

Table 1.1-1. Objectives and relative endpoint

| OBJECTIVES   | ENDPOINTS   | JUSTIFICATION FOR ENDPOINTS   |
|--|---|---|
| Primary  |   |   |
| Can Almega® PL
supplement decrease
triacylglycerides in a
generally healthy
population?  | Triglyceride change from baseline over 6-month period.  | Triglyceride levels is an
atherogenic lipid and an
important risk factor in
cardiovascular disease   |
| Secondary  |   |   |
| Can Almega® PL supplement replicate the decrease in VLDL and total cholesterol we observed in our previous clinical trial (Rao et al., 2020)? Will the results from a controlled population translate to the iwi costumers? Can Almega® PL | Total Cholesterol change from baseline over 6-month period. VLDL-Cholesterol change from baseline over 6-month period. LDL-Cholesterol change from baseline over 6-month period. HDL-Cholesterol change from baseline over 6-month period. hs-CRP change from baseline over 6-month period. Fasting glucose change from baseline over 6-month period. HbA1c change from baseline over 6-month period. | Cholesterol in plasma levels is atherogenic and a risk factor in cardiovascular disease. Hs-CRP is an age-related inflammatory market. Omega-3 help regulate the inflammatory response. |

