### 2.4. General definitions Investigational Product

### and study treatment

- Investigational Product refers to Iwi/Cholesterol supplement, a commercially available capsule-form herbal (algae) supplement containing Almega®PL, a Nannochloropsis algaederived extract rich in eicosapentaenoic acid (EPA). EPA is a type of omega-3 essential fatty acid known to play a beneficial role in protection against cardiovascular disease. Iwi/Cholesterol is the only source of long chain omega-3 that does not contain the DHA that is present in other omega-3 sources (fish oil, krill oil, other algal oils). Almega®PL was registered at the Food and Drug Administration (FDA) as a New Dietary Ingredient (NDIN) in 2014.
- *Study treatment* = 1000-1100 mg/day investigational product (Almega®PL).

Table 2-1. Treatment plan

| Study Stage                                      | Specific
Timing                          | Activity  |  |  |
|--|---|---|--|--|
| Planning
2 Months                             | N/A   | 
 
Approval of protocol
 
Independent peer-review
 
Logistical arrangements
 
Recruitment
 
   |  |  |
| Pre-Study
1 Month                             | Upon approval and completion of recruitment | Preliminary screening against inclusion and exclusion criteria     Pre-study interview:     Information email and gain informed consent from the participant     Enrolled participants purchase the product and receive the testing kits along with instruction regarding the study requirements. |  |  |
| Study
Week 0-24                               | First test kit will be shipped to imaware   |   |  |  |
| Trial  | Trial Period                                | 
 
Participant takes product as instructed
 
Participant will receive and send the test kits on month 3 and 6
 
   |  |  |
| Months 0-6
(Period begins at
trial week 2) |   | Participant completes end-trial blood test.   |  |  |

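### The objectives claim effectiveness and replication of a placebo-controlled result, but one open-label arm with no comparator supports only a within-person change from baseline

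*Protocol*

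**What the plan says.** The overall aim appears in both documents. The SAP (1.1, Study objectives and endpoints) has: "The aim of this study is to assess the effectiveness of Almega®PL on improving blood markers associated with heart health of iwi customers". The Protocol then makes the aim confirmatory: "Specifically, we would like to confirm the decrease in cholesterol observed in our previous trial". A secondary objective asks whether the supplement can "replicate the decrease in VLDL and total cholesterol we observed in our previous clinical trial". Protocol 8.3 (Background) describes that trial as a "double-blind, placebo-controlled, randomized three-month clinical trial".

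The design is given in Protocol 9: "This post-market open label single armed trial involving 200-300 male and female participants". The primary endpoint is "Triglyceride change from baseline over 6-month period", and the secondary endpoints have the same form. Baseline is compared with month 3 and month 6 (Protocol 9; SAP 1.1, Study design). No concurrent, historical or external control is named. Both documents nevertheless speak of differences between groups and say that an intervention effect will be tested by ANCOVA.

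On what participants know, Protocol 8.3.2 lists as a benefit of taking part: "Provides each participant with their lipid panel information they could monitor during the study". The only measure against behaviour change is a request in Protocol 9 to keep diet and physical activity as usual.

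**The concern.** The earlier result was a contrast between randomised arms. The result here will be a contrast between two times in the same people. Influences common to everyone cancel in the first contrast and are carried in full by the second. If lipids fall because participants react to their own results, the analysis counts that fall as a product effect, and the objectives invite a report of effectiveness and of confirmation of the earlier trial.

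The choice of test does not cure this. A correctly paired analysis would measure the change more precisely but could not say what caused it. The primary triglyceride objective and the cholesterol replication objective are both affected.

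**Working it through.** **1. The plan's own figure.** SAP 3 gives N = 210 for a t-test on two independent samples, effect size 0.5, allocation 1:1, power 95%. No alpha is stated there; I assume 0.05 two-sided. The noncentral t calculation gives 105 per group, 210 in total, power 0.9501, so the figure reproduces. It does so only as 105 + 105 in two groups, which this study does not have.

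**2. What each design estimates.** Let P be the product effect and D the average change that would have occurred anyway.
- Earlier trial: (P + D) − D = P, if D is the same in both arms.
- This trial: mean change = P + D.

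Nothing in the plan estimates D. The bias in the mean change as an estimate of P is therefore D, at any sample size and any p-value. With one arm, the ANCOVA has no treatment term; adjusting for baseline does not remove D.

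**3. How often D alone would be significant.** Set P = 0. Inputs:
- N = 210 (SAP 3).
- Thresholds 0.05 (both documents) and 0.05/20 = 0.0025 (SAP 1.1, Study design).
- Drift of 0.20 SD of the change: assumed.
- Within-person correlation r of 0.5 to 0.7: assumed. The documents give neither drift nor correlation.

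*Paired t-test.* Noncentrality = 0.20 × √210 = 2.898. Critical t on 209 df is 1.971 at 0.05 and 3.060 at 0.0025.

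*Planned Welch test applied to the same people.* In units of the single-measurement SD, the drift is d = 0.20 × √(2(1 − r)). The statistic has mean m = d × √(N/2) and, because the pairing is ignored, standard deviation s = √(1 − r). The upper-tail rejection probability is 1 − Φ((c − m)/s); the lower tail is negligible. Here c = 1.966 at 0.05 and 3.042 at 0.0025.
- r = 0.5: d = 0.200, m = 2.049, s = 0.707
- r = 0.7: d = 0.155, m = 1.587, s = 0.548

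| Test | p < 0.05 | p < 0.0025 |
|---|---|---|
| Paired | 0.823 | 0.438 |
| Welch, r = 0.5 | 0.547 | 0.080 |
| Welch, r = 0.7 | 0.245 | 0.004 |

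At the upper planned size of 300, the paired figures rise to 0.932 and 0.661. A larger study makes a false attribution more likely.

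**4. Scale.** If the SD of the change in log-triglycerides is 0.3 to 0.4 (assumed), a drift of 0.20 SD is a fall of 1 − exp(−0.06) = 5.8% to 1 − exp(−0.08) = 7.7%.

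**The case against.** The single arm is openly declared. Protocol 8.3.3 calls the study a cohort in which a population is monitored, and one secondary question asks whether controlled results carry over to customers, which a before-after study can describe. No passage fixes the wording of the final report. All of this is true, but the cohort remark is made about risk to participants, and neither it nor any other passage limits the conclusion. Declaring a design does not make it able to confirm a placebo-controlled result.

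A reader might infer more than the documents support:
- *Regression to the mean.* People may subscribe after a high reading, but no lipid entry criterion is stated. Baseline is also a fresh kit, not the reading that prompted the subscription. If within-person correlation is stable, the regression would already have happened by baseline.
- *Season.* Table 2-1 of the SAP times the pre-study stage "Upon approval and completion of recruitment", which could put everyone on one calendar. That schedule is internally disordered, and Protocol 9 accepts applicants by time of application and ships the kit with the first order, which allows staggered starts.
- *Referral.* Out-of-range results lead to referral, but participants then placed on cholesterol-lowering medication are removed from the trial (Protocol 10.6; SAP 2.10). This limits that route.
- *Wrong time point.* The endpoints are worded over 6 months, but month 3, the earlier trial's duration, is measured and compared with baseline.
- *Near-certain false significance.* The high percentages belong to a paired test at 0.05. Under the planned Welch test at 0.0025 they are small. That is no safeguard: they are small because the test ignores the pairing, which also hides real change, and the estimate stays biased.

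**Conclusion.** The concern holds as a mismatch between the objectives and the design. A single arm without a comparator yields a change from baseline that cannot be attributed to the product, and that change cannot confirm or replicate a randomised, placebo-controlled difference. The firmest documented non-product influence is participants seeing their own results, with only a request to hold diet and activity steady. Season and regression to the mean are possible but not established.

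This conclusion needs no numerical assumption. The frequency of false significance does: it runs from 82% down to 0.4% for the same drift, depending on test, threshold and correlation, and the drift itself is assumed. The percentages are illustrations and do not predict this trial's outcome.

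**What to change.** In Protocol 8.3 (Objectives and Endpoints) and 9, and in both SAP sections numbered 1.1:

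1. Restate the primary and secondary objectives as estimating within-person change from baseline to month 3 and month 6 during the first 6 months of use.
2. Remove the words *effectiveness*, *confirm*, *replicate* and *intervention effect*.
3. State that no causal or replication claim will be made from the change alone, and name the missing comparator and the participants' sight of their results as limitations.

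Optionally, report the month-3 change in total and VLDL cholesterol, with its confidence interval, beside the month-3 changes in both arms of the earlier trial. Label this descriptive and non-concurrent, and attach no pass/fail rule for replication: a bare comparison with the earlier placebo arm has no margin and ignores uncertainty.

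An analysis of weight-stable participants should not be relied on to rule out behaviour change. It conditions on a post-baseline variable, and repeat weighing is not clearly established: Protocol 9 lists weight among the items recorded over the study, but SAP 2.9.1 names only baseline weight. If weight is in fact re-measured, such an analysis can be exploratory only.

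The cost is rewording and, if the option is taken, one table that needs the earlier trial's arm-level results. The real price is a weaker permitted claim.

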10.6. Termination of the Study

This research project may be stopped for a variety of reasons.

During the trial, any participant that records out-of-range analytical levels will be referred to their GP for assessment of suitability/safety for continuation in the trial.

At the discretion of the GP the participant will either be placed on standard care of cholesterol-lowering medication (and removed from the trial) or continue in the trial on the supplementation.

The participant also has the option to stop supplementation at any point.

11. Investigator Benefits

The investigators are being remunerated to conduct this study. They will not allow a conflict of interest to compromise their position or this research study.

12. Consent

The Principal Investigator, [name], is required to provide participants with all information regarding the nature and purpose of the research study, risks/benefits, and the possibility of alternative treatment; participants should be given the opportunity to discuss these. It must be stated that participants are free to withdraw anytime and that if participants do not participate, they will not suffer any prejudice.

13. Advice and Information - Contact Details

If participants have any further questions regarding this study, please do not hesitate to contact:

[name] –Trial Contact Ph: [contact]

24hr [contact]

If unwarranted side effects occur, please don't hesitate to contact a doctor and the study representative. In the case of an emergency please dial 911.

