### 2.9. Patient disposition, disease history and medical history

### 2.9.1. Basic health and background data

Health and baseline disease characteristics data, as characterized by the questionnaire will be summarized and listed. Categorical data, (e.g., gender, smoking, level of physical activity, medication use, etc.) will be summarized and the percentage of participants who answer "yes" to the set questions will be calculated. Continuous data, e.g., age, weight, height, body mass index, will be summarized by descriptive statistics (N, mean, median, standard deviation, minimum and maximum). BMI (kg/m2) will be calculated as weight[kg] / (height[m]2) using weight at Baseline.

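### Apart from iwi itself, no omega-3 product or lipid-lowering drug is screened for or held stable, so the single-arm triglyceride change can be biased either way

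*Protocol*

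**What the plan says.** **Entry.** Protocol section 9, repeated in SAP section 1.1 (Study design), screens for new users: "Any participant who is already using iwi will not be considered in the study". It also disqualifies "Any participant that has a serious condition (including but not limited to kidney, neurological, immunological, liver, and gastrointestinal disease, any heart condition, or diabetes", and adds: "Any participant attempting conception, pregnant or breastfeeding will also be disqualified". The rule then closes: "All other participants will be accepted into the limited study based on their time of application until the quota is completed". Other omega-3 products are not mentioned there, although Protocol section 8.2 refers to the DHA "present in other omega-3 sources (fish oil, krill oil, other algal oils".

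**During the trial.** The stability instruction covers two things: "Participants will be asked to maintain their usual level of physical activity and diet for the duration of the study". Protocol section 10.6 and SAP section 2.10 send participants with out-of-range results to their GP, after which they will "either be placed on standard care of cholesterol-lowering medication (and removed from the trial) or continue in the trial on the supplementation".

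**Data and analysis.** SAP section 2.9.1 summarises questionnaire items ("e.g., gender, smoking, level of physical activity, medication use, etc") as the percentage answering yes. SAP sections 2.7.1 and 2.7.2 define the per-protocol and ITT sets by the number of tests completed. The ANCOVA adjusts for baseline parameters that neither document lists. The primary endpoint is triglyceride change from baseline over 6 months in a single arm.

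**The concern.** The primary result rests on each participant's later triglycerides set against the same person's baseline. A control arm would share any background use of other lipid-active products; here nothing does. Two kinds of participant matter.

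- **Switchers.** A new subscriber who already takes fish, krill or another algal oil is eligible and may swap one product for the other. The baseline is then already a value under omega-3, and the change understates what the product would do in someone not taking omega-3.
- **Changers.** Someone who starts or intensifies another omega-3 or a lipid drug after baseline adds that effect to the product's. Someone who stops one subtracts it.

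The study may itself prompt such changes. Protocol section 8.3.2 lists access to one's own lipid panel during the study as a benefit, and section 10.4 directs people with out-of-range results to medical professionals. If this information is not collected, nobody can later show which influence was larger.

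**Working it through.** **1. What the text covers**

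| Situation | Covered by the plan? |
|---|---|
| Already using iwi | Excluded |
| Other omega-3 at entry | Not asked, not excluded |
| Lipid drug at entry | Not excluded; medication use summarised only |
| GP starts cholesterol-lowering drug after out-of-range result | Removed from trial |
| Lipid drug started by another route, changed in dose, or stopped | No provision |
| Other omega-3 started or stopped | No provision |

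The removal rule does not carry into the analysis sets. A participant removed after the month-3 test has two tests and still meets the SAP ITT definition. Whether the month-3 value pre-dates the drug is not something the plan would record.

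**2. The plan's own figure.** SAP section 3 gives 210 for a two-independent-sample t-test with effect size 0.5, ratio 1 and 95% power. Taking two-sided 0.05 from the analysis text (section 3 states no alpha), the exact noncentral t gives 105 per group, 2 × 105 = 210, power 0.950. It reproduces and does not depend on this point. Below, 210 is used as the number of participants, within the planned 200 to 300.

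**3. Dilution by switchers (assumed shares).** If a fraction f switch at similar intake and show no further change, the measured effect is (1 − f) × the true effect. For a true standardised change of 0.25, a paired t-test with n = 210, mean (1 − f) × 0.25 and SD √(1 + f(1 − f) × 0.25²) gives:

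| f | Mean change | Power at 0.05 | Power at 0.0025 |
|---|---|---|---|
| 0 | 0.25 | 0.95 | 0.71 |
| 10% | 0.225 | 0.90 | 0.58 |
| 20% | 0.20 | 0.82 | 0.43 |
| 30% | 0.175 | 0.71 | 0.30 |

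With a true change of 0.5, power at 0.05 stays at or above 0.988 up to f = 40%, but the estimate is diluted in the same proportion.

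**4. Inflation by changers (assumed shares and shifts).** True product effect zero; a share p have triglycerides lowered by D standard deviations of change through another treatment. Mean shift pD, SD √(1 + p(1 − p)D²), paired test, n = 210:

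| p | D | Mean shift | Chance of p < 0.05 | Chance of p < 0.0025 |
|---|---|---|---|---|
| 5% | 0.5 | 0.025 | 0.065 | 0.004 |
| 10% | 0.5 | 0.05 | 0.11 | 0.010 |
| 20% | 0.5 | 0.10 | 0.29 | 0.053 |
| 10% | 1.0 | 0.10 | 0.28 | 0.049 |
| 20% | 1.0 | 0.20 | 0.76 | 0.36 |

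**5. Net direction.** With separate groups, net bias towards benefit is about pD − f × (true effect). For p = 10%, D = 0.5, f = 20% and a true effect of 0.25, this is 0.05 − 0.05 = 0. Modest changes in either share tip the sign.

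**6. Dependence on the test.** The plan names Welch or rank-sum tests, which are unpaired. As an illustration, assume an SD of percentage change of 30% and 10% of participants with a 20% fall from other treatment. Then SE = 30%/√210 = 2.07%, shift = 10% × 20% = 2%, and 2/2.07 = 0.97 SE. A paired test of an inert product rejects with probability about 0.16 at 0.05 and about 0.020 at 0.0025. For a Welch test at 0.05, the effective cut-off in paired SE units is 1.96/√(1 − r), where r is the assumed baseline to follow-up correlation. Rejection is then about 8.5%, 3.6% and 1.6% for r = 0.3, 0.5 and 0.6, against 1.9%, 0.6% and 0.2% without the shift. The shift raises the rate in each case, but no single figure describes this plan.

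**The case against.** **The study monitors customers as they come.** Protocol section 8.3.3 calls it a cohort of people who would take the product anyway, and one objective asks whether controlled results carry over to iwi customers. Switchers belong to that population, and refusing them would change the question. This stands, and it argues for flagging rather than exclusion. It does not remove the need for the data, because the primary question asks whether the supplement lowers triglycerides.

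**Other rules already help.** Excluding any heart condition and diabetes plausibly removes some lipid-drug users, and the GP rule closes one important route. Both stand. A reader who infers that nothing but iwi use is screened, or that lipid drugs can change freely, goes further than the text. Raised lipids are not a listed exclusion, however, and the GP rule is silent on omega-3 products, dose changes and stopping.

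**Medication use is collected, and the contacts may pick up more.** The SAP does not say how often the questionnaire is given, the follow-up email concerns adherence to the protocol generally, and the unspecified ANCOVA covariates could include medication. So it would be too strong to say that no analysis will use these data; what can be said is that none is stated to. Protocol section 10.1 also refers to inclusion and exclusion criteria, and no separate list appears in the text available.

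**Excluding people who change treatment has its own bias.** Those who start lipid drugs may be those whose triglycerides are high or rising, and removing them can favour the product. This stands and shapes the fix.

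**Conclusion.** The gap is real: followed as written, the plan can give a biased triglyceride change and would hold no record from which to judge it. That no screen or tracking is stated is clear from the text. The size is not. Dilution is about the fraction who switch, if intake is similar and they show no further change; inflation is the share changing treatment times the effect of that change. Both shares and the size of the shift are assumptions, and the two can cancel.

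Three stronger readings are not supported. A reader might infer that the result is contaminated; the documents give no prevalence, so only that it can be biased. A reader might count any lipid-drug user as a problem; a drug taken unchanged throughout is present in both measurements and does not by itself bias the within-person change. A reader might take about 16% as this trial's false-positive rate; that value needs a paired test at 0.05 and an assumed net one-directional shift, whereas the plan names unpaired tests and the SAP a 0.0025 threshold.

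**What to change.** 1. **Screening questionnaire.** Add two items: current or recent use of any omega-3 product other than iwi, and any recent start, stop or change of lipid-lowering medication. State the look-back period. Enrol and flag those who answer yes, so the customer population is unchanged.
2. **Follow-up.** Ask the same two questions at the month-3 and month-6 adherence contacts already planned, with dates, so that each test result can be placed before or after a change.
3. **SAP.** Keep the full-set triglyceride estimate as primary and pre-specify two sensitivity analyses: (a) participants with no other omega-3 use and no recent lipid-drug change at baseline; (b) the same set, also leaving out those with changes during follow-up. Report the numbers left out of each, and note for (b) that selecting on post-baseline events can itself favour the product. State how participants removed under the GP rule are handled in the ITT set.

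The cost is two questionnaire items, two lines in existing contacts, two extra analyses, and sensitivity sets smaller than the full set. Recruitment is unaffected. Exposure history not asked for at the time can later be recovered only by recall.
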